**Table 3. Markers to be probed and assessed in blood and tissues**

Progenitor cell markers	CD133, CD45, podoplanin, CD90, NG2
Lymphatic endothelial cell markers	VEGFR-2, VEGFR-3, podoplanin, Prox1, LYVE1
Beta-adrenergic receptors	Beta-1, beta-2, beta-3 adrenergic receptors
Macrophage markers	CD68, iNOS, F4/80

These analyses have been optimized and validated using discarded de-identified involved and uninvolved LM specimens. Fixed frozen tissue will be prepared and 5-micron sections generated. Standard immunohistochemistry will be performed with commercially available antibodies and H&E staining performed. Results will be captured by microscopy and digital camera. Results will be quantified using ImageJ software and *Student's t-test* to determine significance, with a  $p < 0.05$  considered significant. We have already isolated similar specimens from  $> 10$  patients and have obtained consistent results using these methodologies.

Analysis of circulating biomarkers will also be done. Identification of pertinent circulating biomarkers of a positive response will aid in future studies and minimize the need for more invasive procedures. We will use FACS to determine if LMPCs double positive for podoplanin and CD90 are in circulation. Expression of circulating VEGFR-2 and VEGFR-3 will also be assessed as it has been reported that propranolol reduced circulating VEGFR-3 levels in a patient with a generalized lymphatic anomaly[18].

## **3.0 SCREENING AND STUDY ENROLLMENT PROCEDURES**

### **3.1 General Guidelines**

Eligible patients will be registered on-study at Columbia University by the Study Coordinator. The required forms (Eligibility Screening Worksheet and Study Registration Form) can be found in Appendix 1.

**Following registration, patients should have baseline evaluations (physical examination, EKG, MRI, blood draw and tissue biopsy—see Table 8) before beginning protocol treatment within 14 days.** Issues that would cause treatment delays should be discussed with the Principal Investigator. If a patient does not receive protocol

therapy following registration, the patient's registration on the study may be canceled. The Study Coordinator should be notified of cancellations as soon as possible.

### 3.2 Patient Registration

To register a patient, the following documents should be completed by the research nurse, PI, or co-Investigator and faxed [[contact]] or e-mailed [[contact]] to the Study Coordinator/Data Manager:

- Copy of required laboratory and radiology tests
- Signed patient consent form
- HIPAA authorization form
- *Other appropriate forms (e.g., Eligibility Screening Worksheet, Registration Form)*

To complete the registration process, the Study Coordinator will:

- Assign a patient study number.
- Register the patient on the study.

## 4.0 PATIENT ELIGIBILITY

Baseline evaluations are to be conducted within 2 weeks (14 days) prior to start of protocol therapy. In the event that the patient's condition is deteriorating, laboratory evaluations should be repeated within 48 hours prior to initiation of the next dose escalation of propranolol.

**Important note: The eligibility criteria listed below are interpreted literally and cannot be waived. All clinical and laboratory data required for determining eligibility of a patient enrolled on this trial must be available in the patient's medical or research record which will serve as the source document for verification at the time of audit.**

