### 4.1 Inclusion Criteria

- 4.1.1 Age: Patients must be  $\geq 12$  years of age at the time of study enrollment.
- 4.1.2a Diagnosis: Patients must have a clinically, pathologically, and/or radiographically diagnosed (lymphscintogram or MRI) lymphedema affecting an extremity without prior surgical intervention or major trauma at that extremity.
- 4.1.3 Disease Status: Patients must have either measurable or evaluable disease (see Sections 12.2 and 12.3 for definitions).
- 4.1.4 Therapeutic Options: Patient's current disease state must be one for which there is no known curative therapy or therapy proven to prolong survival with an acceptable quality of life.
- 4.1.5 Performance Level: Karnofsky  $\geq 50\%$  for patients  $> 16$  years of age and Lansky  $\geq 50$  for patients  $\geq 12$  to  $\leq 16$  years of age. Patients who are unable to walk because of paralysis, but who are up in a wheelchair, will be considered ambulatory for the purpose of assessing the performance score.
- 4.1.6 Prior Therapy  
Prior therapy may have included surgery or interventional radiology procedures,

but must have occurred  $> 4$  weeks prior to baseline imaging studies and study entry. Prior therapy may have included other investigational drugs (e.g. sirolimus, sildenafil), since there are no standard medical therapies for lymphedema, but must have concluded  $> 4$  weeks prior to baseline imaging studies.

4.1.7 **Organ Function Requirements**

These are required for enrolled patients with LMs.

4.1.7.1 Adequate Bone Marrow and Renal Function Defined as:

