**4.2 Exclusion Criteria**

4.2.1 Patients with secondary lymphedema.

4.2.2 Patients who have had surgery or interventional radiology treatment within 4 weeks prior to baseline imaging studies and/or study entry, or those who have not recovered from these interventions.

4.2.3 Patients who are receiving any other investigational agents.

4.2.4 Patients with known contraindications to propranolol therapy, or a history of allergic, hypersensitive, or adverse reaction to propranolol.

- 4.2.5 History of allergic reactions attributed to compounds of similar chemical or biologic composition to propranolol.
- 4.2.6 Patients requiring treatment with drugs known to interact with propranolol including those with other cardiovascular drugs (e.g. antiarrhythmics, calcium channel blockers); migraine drugs; theophylline; neuroleptic, anti-ulcer, and lipid-lowering drugs; and warfarin.
- 4.2.7 Patients must be able to swallow capsules or liquid.
- 4.2.8 Patients who in the opinion of the investigator may not be able to comply with the safety monitoring requirements of the study are not eligible.
- 4.2.9 Uncontrolled intercurrent illness including, but not limited to, ongoing or active infection; asthma, reactive airway disease, or bronchospasm requiring medication; ulcers or nonhealing wounds of the lymphatic malformation; symptomatic congestive heart failure, pericardial effusion, cardiac arrhythmia; or psychiatric illness/social situations that would limit compliance with study requirements.
- 4.2.10 Other contraindications including pheochromocytoma, bradycardia, first degree heart block, decompensated heart failure.

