### **12.0 EVALUATION CRITERIA**

#### 12.1 **Adverse Events**

Any patient who receives the study drug will be evaluable for Adverse Effects. This study will utilize the NIH Common Terminology Criteria for Adverse Events v4.0 (CTCAE) for evaluating adverse events.

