#### 12.2 **Disease Parameters**

Measurable disease: Measurable lesions are defined as those that can be accurately measured in at least one dimension (longest diameter to be recorded) as  $> 50$  mm by clinical exam and MRI. All measurements must be recorded in millimeters (or decimal fractions of centimeters).

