#### 12.3 **Methods for Evaluation of Measurable Disease**

All measurements should be taken and recorded in metric notation using a ruler, measuring tape, or calipers. All baseline evaluations should be performed as closely as possible to the beginning of treatment.

The same method of assessment and the same technique should be used to characterize

each identified and reported lesion at baseline and during follow-up.

Clinical lesions: The circumference of the affected (vs. unaffected) extremity will be documented in the patient's clinical chart along pre-determined landmarks), as this is a standard part of care for patients with extremity LM. Landmarks include: midway point between ASIS (anterior superior iliac spine) to the patella for the thigh, and midway point between patella to the medial malleolus for lower extremities. The midway point between the axillary crease to medial epicondyle (upper arm) and midway point between medial epicondyle to hamate bone of the wrist (forearm) for upper extremities.

MRI and QMR have excellent contrast, spatial, and temporal resolution. The same scanner should be used and the image acquisition protocol should be followed as closely as possible to prior scans. While CT scans may give even improved spatial resolution, MRI has the advantage of no ionizing radiation, gives superior soft tissue resolution, and allows for multi-planar imaging.

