##### 12.4.1 Definitions

Subjective Response: Patients who complete at least the questionnaires at baseline (study entry) and at the last study visit will be included for subjective evaluation.

Evaluable for Objective Response: by physical examination and radiological studies as outlined above.

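### Table 4 prints the hemoglobin entry limit in mg/dl, so the only bone-marrow criterion screens out nobody when read literally, as section 4.0 requires

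*Combined protocol and SAP*

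**What the plan says.** Section 4.0 sets the standard for all the entry criteria: "The eligibility criteria listed below are interpreted literally and cannot be waived". It adds that the data behind each eligibility decision must be in the patient's record for checking at audit.

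Item 4.1.7.1 asks for adequate bone marrow and renal function and leaves the definition to Table 4. The table has three rows: hemoglobin, at least 8 mg/dl; creatinine, within normal limits and below 1.2, with no unit; and, as the alternative to the creatinine row, a creatinine clearance limit with its unit stated. Only the hemoglobin row concerns bone marrow.

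Two other items in section 4 bear on the point:

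- Item 4.2.7 stands under the heading "4.2 Exclusion Criteria" and reads: "Patients must be able to swallow capsules or liquid".
- Item 4.1.3 reads: "Patients must have either measurable or evaluable disease (see Sections 12.2 and 12.3 for definitions". Section 12.2 offers: "Measurable lesions are defined as those that can be accurately measured in at least one dimension", with a size above 50 mm. Section 12.3 is about technique, for example: "All measurements should be taken and recorded in metric notation using a ruler, measuring tape, or calipers".

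**The concern.** An entry limit is a decision threshold. The protocol forbids waivers and asks for literal reading, so a wrong unit cannot simply be put right by judgement at the screening visit. A site that follows the text exactly has no hemoglobin criterion at all. A site that applies the number with another unit departs from the text that an auditor would use. The first case is the one that bears on safety, because the item exists to keep out patients whose marrow function is inadequate.

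The same literal-reading rule draws attention to the other two items. One is a requirement filed among the exclusions. The other sends the reader to a definition that is not there.

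**Working it through.** **Hemoglobin.** The one input is the Table 4 limit of 8 mg/dl. The conversion is 1 g = 1000 mg.

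- Printed limit in g/dl: 8 / 1000 = 0.008 g/dl.
- If the same number had been meant in g/dl: 8 × 1000 = 8000 mg/dl. The ratio to the printed limit is 8000 / 8 = 1000.

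The table below applies the printed limit, and the same number read in g/dl, to a range of illustrative values.

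| Hemoglobin (g/dl) | In mg/dl | Meets 8 mg/dl as printed | Would meet 8 g/dl |
|---|---|---|---|
| 1 | 1000 | yes | no |
| 2 | 2000 | yes | no |
| 4 | 4000 | yes | no |
| 6 | 6000 | yes | no |
| 7.9 | 7900 | yes | no |
| 8 | 8000 | yes | yes |
| 12 | 12000 | yes | yes |

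Even the lowest value, 1 g/dl, is 1000 / 8 = 125 times the printed limit. The criterion as printed therefore separates no one from anyone.

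**Item 4.2.7.** No arithmetic applies. The list under 4.2 has no opening stem saying that patients are excluded if an item is true. It mixes noun phrases with full sentences that carry their own sense. Item 4.2.8, for instance, ends by saying that the patients it describes are not eligible, so it would become a double negative if the heading reversed every item. Item 4.2.7 is likewise a complete sentence and states a requirement. It is in the wrong list, but its meaning survives.

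**Item 4.1.3.** It names two routes, measurable and evaluable, and refers to two sections.

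- Section 12.2 defines measurable disease only.
- Section 12.3 gives measuring methods, including limb circumference at named landmarks on the affected and unaffected sides. It does not say what makes disease evaluable.
- The word occurs elsewhere in other senses. Section 12.1 uses it for safety: "Any patient who receives the study drug will be evaluable for Adverse Effects". Section 12.4.1 uses it for response: "Evaluable for Objective Response: by physical examination and radiological studies as outlined above". Neither describes disease at entry.

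The measurable route can be applied. The evaluable route has no definition to apply.

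**The case against.** The strongest reply is that the unit is an obvious slip. The row sits under a heading about adequate bone marrow function, so a limit that everyone passes cannot have been intended, and staff would read it sensibly. The Eligibility Screening Worksheet in Appendix 1, which is not among the documents reviewed, may carry the right unit. Nothing in the documents suggests that a severely anemic patient would in fact be enrolled. All of that is fair, and it limits the claim to what the text says. It does not remove the point: section 4.0 rules out reading by intent, and a worksheet with a different limit would contradict the protocol.

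Two stronger readings are tempting, and the documents do not support either.

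- A reader might infer that 4.2.7, as a listed exclusion, shuts out nearly every candidate. That needs an exclusion stem that section 4.2 does not have. The sentence still says what it means.
- A reader might infer that the hemoglobin error makes the response analysis set in section 11.5 disputable, since that set is built on meeting the eligibility criteria. A limit that fails nobody removes nobody from the set, so this does not follow.

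On 4.1.3, it is fair to say that the measurable route works, that 12.3 already describes limb girth, and that 4.1.2a separately requires diagnosed lymphedema of an extremity. What remains is a missing definition. It could matter only for a patient without disease above 50 mm, and the documents do not say how many such patients to expect.

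**Conclusion.** The hemoglobin limit is wrong as printed. At 0.008 g/dl it excludes nobody, and with it goes the only bone-marrow criterion in 4.1.7.1. The conversion is exact. The factor of 1000 as the size of the error rests on an assumption that the documents do not confirm, namely that 8 was meant in g/dl. That the printed limit screens no one out does not depend on this assumption. It rests only on every patient's hemoglobin being above 0.008 g/dl.

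The misplaced 4.2.7 and the undefined term in 4.1.3 are secondary drafting points and do not change results. Nothing here touches sample size, power, type I error or an endpoint. The case for correction is that an entry safeguard has no effect as written, and that the repair is simple.

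**What to change.** In one amendment:

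- **Table 4.** The sponsor confirms the intended hemoglobin unit and value and corrects the row. The same correction goes into the Eligibility Screening Worksheet if it repeats the text. The creatinine limit is given its unit.
- **Item 4.2.7.** Move it to section 4.1, or reword it as an exclusion of patients who are unable to swallow the drug.
- **Item 4.1.3 with 12.2 and 12.3.** Reconcile the three. Either define evaluable disease, for which the limb circumference in 12.3 and MRI are already collected, or delete the term.

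The cost is a short text change and a check of the screening form. No new procedure or change in sample size is needed. Deleting the evaluable route could narrow entry if any patient was expected to qualify by it. The documents give no count, so the sponsor should consider this before choosing deletion over definition.

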### 4.1 Inclusion Criteria

- 4.1.1 Age: Patients must be  $\geq 12$  years of age at the time of study enrollment.
- 4.1.2a Diagnosis: Patients must have a clinically, pathologically, and/or radiographically diagnosed (lymphscintogram or MRI) lymphedema affecting an extremity without prior surgical intervention or major trauma at that extremity.
- 4.1.3 Disease Status: Patients must have either measurable or evaluable disease (see Sections 12.2 and 12.3 for definitions).
- 4.1.4 Therapeutic Options: Patient's current disease state must be one for which there is no known curative therapy or therapy proven to prolong survival with an acceptable quality of life.
- 4.1.5 Performance Level: Karnofsky  $\geq 50\%$  for patients  $> 16$  years of age and Lansky  $\geq 50$  for patients  $\geq 12$  to  $\leq 16$  years of age. Patients who are unable to walk because of paralysis, but who are up in a wheelchair, will be considered ambulatory for the purpose of assessing the performance score.
- 4.1.6 Prior Therapy  
Prior therapy may have included surgery or interventional radiology procedures,

but must have occurred  $> 4$  weeks prior to baseline imaging studies and study entry. Prior therapy may have included other investigational drugs (e.g. sirolimus, sildenafil), since there are no standard medical therapies for lymphedema, but must have concluded  $> 4$  weeks prior to baseline imaging studies.

4.1.7 **Organ Function Requirements**

These are required for enrolled patients with LMs.

4.1.7.1 Adequate Bone Marrow and Renal Function Defined as:

**Table 4. Organ Function Criteria**

Hemoglobin	$\geq 8$ mg/dl
Creatinine	Within normal limits ( $<1.2$ )
	OR
Creatinine Clearance	$\geq 60$ mL/min/1.73 m  for patients with creatinine levels above institutional normal

4.1.7.4 **Adequate Cardiac Function Defined as:**

- Baseline heart rate and blood pressure on physical exam within age-defined normal ranges\*
- Normal cardiac rhythm by electrocardiogram
- Normal intracardiac anatomy, pericardial space, and function by echocardiogram (if indicated by screening cardiologist)

\*See Appendix 7.

4.1.7.5 **Adequate Pulmonary Function Defined as:**

- No evidence of dyspnea at rest, no exercise intolerance, and a pulse oximetry  $> 94\%$  if there is clinical indication for determination.

4.1.8 **Pregnancy:** A negative pregnancy test must be obtained in girls who are post-menarchal. Males or females of reproductive potential may not participate unless they have agreed to use an effective contraceptive method.

4.1.9 **Informed Consent:** All patients and/or their parents or legal guardians must sign a written informed consent. Assent, when appropriate, will be obtained according to institutional guidelines.

**4.2 Exclusion Criteria**

4.2.1 Patients with secondary lymphedema.

4.2.2 Patients who have had surgery or interventional radiology treatment within 4 weeks prior to baseline imaging studies and/or study entry, or those who have not recovered from these interventions.

4.2.3 Patients who are receiving any other investigational agents.

4.2.4 Patients with known contraindications to propranolol therapy, or a history of allergic, hypersensitive, or adverse reaction to propranolol.

- 4.2.5 History of allergic reactions attributed to compounds of similar chemical or biologic composition to propranolol.
- 4.2.6 Patients requiring treatment with drugs known to interact with propranolol including those with other cardiovascular drugs (e.g. antiarrhythmics, calcium channel blockers); migraine drugs; theophylline; neuroleptic, anti-ulcer, and lipid-lowering drugs; and warfarin.
- 4.2.7 Patients must be able to swallow capsules or liquid.
- 4.2.8 Patients who in the opinion of the investigator may not be able to comply with the safety monitoring requirements of the study are not eligible.
- 4.2.9 Uncontrolled intercurrent illness including, but not limited to, ongoing or active infection; asthma, reactive airway disease, or bronchospasm requiring medication; ulcers or nonhealing wounds of the lymphatic malformation; symptomatic congestive heart failure, pericardial effusion, cardiac arrhythmia; or psychiatric illness/social situations that would limit compliance with study requirements.
- 4.2.10 Other contraindications including pheochromocytoma, bradycardia, first degree heart block, decompensated heart failure.

## **5.0 TREATMENT PROGRAM**

### **5.1 Overview of Treatment Plan**

Patients will be provided with propranolol prescriptions. Dosing is weight-based (corrected to the closest 10kg increment) and will be prescribed by the PI after medical evaluation by the study cardiologist.

The starting dose of propranolol will be 0.5 mg/kg/day, which is the current institutional dose for initial treatment for cardiovascular and hemangioma indications in children. Dose escalation to 1 mg/kg/day will take place at the 2-week evaluation in the absence of clinical contraindications. If patient tolerates 1 mg/kg/day dose, they will be escalated to 2 mg/kg/day at the 4-week evaluation. In the absence of clinical contraindications, dose escalation will be increased to 3mg/kg/day at week 6 and continued for the duration of the study. A maximum of 8-weeks of therapy may be administered.

### **5.2 Dose Escalation Schema**

#### **5.2.1 Inter-Patient Escalation**

There is no inter-patient escalation allowed on this study.

#### **5.2.2 Intra-Patient Escalation**

The starting dose will be 1 mg/kg/day (BID) with dose escalation up to 3 mg/kg/day (BID) in the absence of clinical contra-indications. There will be no escalations beyond 3 mg/kg/day (Table 1).

At the return visit, patients must have no evidence of clinical contraindications with normal HR and BP parameters prior to dose escalation occurring. They will be re-evaluated 2 hours after the first escalated dose. If individuals have normal heart rate and blood pressure and report no clinical symptoms (dizziness, increased fatigue), they will be given the new escalated dose and re-evaluated 2 hours after the new dose. If their HR and BP are within normal limits (WNL), they will be sent home on this new escalated dose and will return in another 2 weeks for evaluation. If individuals are found to have a fall in their blood pressure or heart rate below the normal value at 2 hours after the new dose, they will not be escalated and will be sent home at the current dose. They will return in 2 weeks for evaluation for dose escalation.

If individuals are found to have a fall in their blood pressure or heart rate below the normal value at the return visit *and* clinically asymptomatic, they will be held at the current tolerated dose level (no escalation). If they are able to tolerate this lower dose level with normal parameters and no clinical symptomatology they will return for evaluation of dose escalation at the next visit. If their parameters are WNL, they will be escalated and evaluated. If they do not tolerate dose escalation, they will be held at the current tolerated dose of propranolol until the end of the study without further attempts to escalate. Patients who are not able to tolerate dose escalation at 2 consecutive visits will have no more dose escalation challenges and stay for the remainder of the study at the current tolerated dose.

Individuals found to have a fall in HR and BP below normal parameters at initiation (0.5mg/kg/day, week 1) will be removed from the study for 1 week. At week 2 they will be re-evaluated. If HR and BP are within normal parameters they will be reintroduced to the study. If patient is once again found to have fall in HR/BP below normal parameters upon an attempt to re-initiate (failed the lowest initiation dose of 0.5mg/kg/day twice), they will be removed from the study.

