At the 2nd-week re-evaluation, they will be escalated to the new dose (1mg/kg/day) if the baselines HR and BP are WNL. Patients will have HR and BP noted after first new dose (1mg/kg/day) of propranolol to ensure that the propranolol is tolerated. If the HR and BP are WNL, they will continue on this new dose and re-evaluated in 2 weeks for the 4th-week evaluation. If they have a drop in HR and BP to below normal range, they will be de-escalated and remain on the prior dose (0.5mg/kg/day) until the next visit (week 4).

At the 4th and 6th-week evaluation, their baseline vitals will be evaluated and their propranolol escalated to the next dose (if vitals are WNL) and have their HR and BP assessed after first new dose. Propranolol will stay increased or held at old dose depending on HR and BP after the first new dose as described above. If on re-evaluation in 2 weeks a patient continues to have below normal HR and blood pressure on re-challenge of the escalated dose, they will not be escalated and remain at the last tolerated dose for the remainder of the 8 week period with no further re-challenges. For patients with below normal HR and BP and needed their doses held, they will be reported as AEs.

At each study visit, patients will be asked to complete validated questionnaire to assess for tolerance to propranolol treatment, subjective changes in lymphedema symptoms, and self-reported function and activities of daily living (SF-36, LYMPH—ICF, and LYMPH—ICF—LL) (See attached documents, Appendix 2). Physical examination will include weight and BMI, vitals (HR, BP), and measurement of girth of normal and affected extremity.

MRIs and blood tests will be performed at study entry and study endpoint to assess for changes in lymphedema tissue composition[21-23] in response to propranolol.

Blood draws will be performed at study entry, at the midpoint, and study endpoint to assess for changes in circulating biomarkers in response to propranolol treatment.

Correlative biomarkers assessed will include markers of progenitor, endothelial, lymphatic, macrophage, and adipocyte cells, and expression of beta-adrenergic receptors (Table 3).

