## 6.0 DOSE MODIFICATIONS FOR ADVERSE EVENTS

**The Study Chair must be notified of any dosage modification.**

### 6.1 Dose Modifications for Potential Propranolol Specific Side Effects

#### 6.1.1 Hypotension and Bradycardia

**Baseline blood pressure (BP)** is defined as the blood pressure obtained at the examination used for study enrollment. This baseline BP should be obtained as follows: 1) Obtain 3 serial blood pressures from the same extremity with the patient in the same position that are separated by at least 5 minutes. Avoid using the lower extremity if possible. BP will not be obtained from the affected limb. 2) Average the systolic blood pressure from the 2nd and 3rd measurements. 3) Average the diastolic blood pressure from the 2nd and 3rd measurements. 4) The baseline BP is the average of the systolic over the average of the diastolic measurements.

Heart rate will be measured by palpation of the radial pulse serially from the same extremity for 15 secs, separated by at least 5 minutes. In the case of extremity LMs, pulse rate will not be obtained from the affected limb. 2) Average the pulse rate from 2nd and 3rd measurements.

6.1.1.1 Patient must have no evidence of clinical contraindications with normal HR and BP parameters prior to dose escalation occurring. If individuals are found to have a fall in their blood pressure or heart rate to below normal limits, but asymptomatic:

- a. patient will be not have dose escalation
- b. patient will be evaluated for dose escalation at the next 2-week cycle.
- c. if HR and BP fall below normal ranges and patient is symptomatic, propranolol will be held for 2 weeks, and re-introduced at the next visit at the lowest tolerated dose.
- d. if patient is at the lowest dose already (0.5mg/kg/day), they will be pulled from the study and re-evaluated at the next visit.
- e. Patients receiving 0.5mg/kg/day who experience HR or BP decrease below the normal range at 4 weeks must be taken off protocol therapy.

Table 5. Side effects and propranolol dosing guidelines

Hypotension and Bradycardia	Propanolol Dosing Guidelines
Within normative range	No change in dose
Below normal range, asymptomatic	Cardiology evaluation, EKG, echocardiogram; if cardiac status is acceptable, patient will not have dose escalation and remain at current dose level with subsequent re-evaluation at 2 weeks

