**14.2.2 Frequency of monitoring**

Patients will be monitored and assessed during their study visits (weeks 1, 2, 4, 6, 8). In addition, patients will be encouraged to contact the PI and/or study coordination if they have any issues, concerns, unexpected symptoms to be assessed.

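### Vital signs that gate escalation (Weeks 2, 4, 6) and those at Week 8 have no set time since the last dose, so near-limit patients can be classified by dose timing; a minor point with a cheap fix

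*Combined protocol and SAP*

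**What the plan says.** Section 2.3.2.1, repeated in 2.4, puts the peak haemodynamic effect at 1 to 3 hours after an oral dose. Section 9.1.6 sets twice-daily dosing in equal parts.

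Two kinds of reading follow.

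- **After an escalated dose.** Section 5.2.2 sets the time: "They will be re-evaluated 2 hours after the first escalated dose". A value below normal at that point stops the escalation.
- **Before escalation, at the return visit.** Section 5.2.2 says "At the return visit, patients must have no evidence of clinical contraindications with normal HR and BP parameters prior to dose escalation occurring", and gives the consequence for asymptomatic patients, who are held at the current dose, under the condition "If individuals are found to have a fall in their blood pressure or heart rate below the normal value at the return visit". Section 2.4 calls the Week 2, 4 and 6 readings baseline values. Neither section says how long after the last home dose they are taken.

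The study schedule (Table 6) and section 14.2.2 place a vital-signs visit at Week 8, again with no time relative to dose. Section 6.1.1 sets limb, position, spacing and averaging, but not time since dose. On the pulse it says "Heart rate will be measured by palpation of the radial pulse serially from the same extremity for 15 secs".

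The consequences of a low value are spread over three places. Table 5, for asymptomatic patients: "Cardiology evaluation, EKG, echocardiogram; if cardiac status is acceptable, patient will not have dose escalation". Item e of 6.1.1.1: "Patients receiving 0.5mg/kg/day who experience HR or BP decrease below the normal range at 4 weeks must be taken off protocol therapy". Section 2.4: "For patients with below normal HR and BP and needed their doses held, they will be reported as AEs".

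**The concern.** The same normal limit is applied to a reading at a known 2 hours and to one that could fall anywhere in the dosing interval. A patient who took the morning dose at home two hours before the visit is read near peak. One who waited is read about 12 hours after the last dose. Close to the limit, that difference alone can decide whether the patient is escalated, sent for cardiac work-up or reported as an adverse event.

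Vital signs are the objective half of the tolerability endpoint in section 11.2.2, and section 8.4 reports toxicity rates for each dose. If time since dose is not recorded, it cannot be reliably recovered at analysis.

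Week 8 gates nothing, but it is the only scheduled reading after two weeks at 3 mg/kg/day. Taken far from the dose, it is less able to show a fall on that dose.

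**Working it through.** The plan states no figure to reproduce. The check has four parts.

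**1. Which readings are timed.** The reading after each escalated dose is timed at 2 hours. Of the four readings on repeated dosing (Weeks 2, 4, 6 and 8), 0 of 4 have a set time. For the first 0.5 mg/kg/day dose, section 2.4 says only that patients are re-evaluated. The hourly advice there and in 2.3.2.1 is a general recommendation about dose increases.

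**2. What one hold costs.** Section 5.1 allows escalation at Weeks 2, 4 and 6 and stops therapy at 8 weeks. In mg/kg/day:

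| Held at | After Wk 2 | After Wk 4 | After Wk 6 |
|---|---|---|---|
| never | 1 | 2 | 3 |
| Week 2 | 0.5 | 1 | 2 |
| Week 4 | 1 | 1 | 2 |
| Week 6 | 1 | 2 | 2 |

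Any single hold leaves the patient at no more than 2 mg/kg/day. With the 15-20 patients of section 11.1, one patient classified differently moves a per-dose rate by 1/20 = 5.0 to 1/15 = 6.7 percentage points, if all contribute at that dose.

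**3. How far timing can move a reading.** The documents give no size for the peak-to-trough difference, so these inputs are assumptions. Let p be the patient's peak-time heart rate minus the limit. Let D be the rise from peak to pre-dose: 0 at peak, and 3, 5 or 10 bpm pre-dose. Let SD be the visit-to-visit standard deviation: 2, 4 or 6 bpm. Then P(read low) = Φ(−(p + D)/SD).

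| p (bpm) | D | SD 2 | SD 4 | SD 6 |
|---|---|---|---|---|
| +2 | 0 (peak) | 0.16 | 0.31 | 0.37 |
| +2 | 3 | 0.01 | 0.11 | 0.20 |
| +2 | 5 | 0.00 | 0.04 | 0.12 |
| +2 | 10 | 0.00 | 0.00 | 0.02 |
| −3 | 0 (peak) | 0.93 | 0.77 | 0.69 |
| −3 | 3 | 0.50 | 0.50 | 0.50 |
| −3 | 5 | 0.16 | 0.31 | 0.37 |
| −3 | 10 | 0.00 | 0.04 | 0.12 |
| +10 | 0 (peak) | 0.00 | 0.01 | 0.05 |
| +10 | 3 | 0.00 | 0.00 | 0.02 |

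At matched SD, the peak and pre-dose readings differ by 15-35 percentage points for p = +2 and by 19-93 points for p = −3 (the Week 8 case). For p = +10 there is almost no difference. These are the two extremes of timing, so real visits would usually differ by less. Blood pressure is not modelled.

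**4. Pulse count (separate and minor).** One beat in 15 seconds is 4 bpm, so the mean of two counts moves in steps of 4/2 = 2 bpm. With 60 seconds the step is 1/2 = 0.5 bpm. The largest counting-error SD is 0.5 × 4/√2 = 1.41 bpm against 0.5 × 1/√2 = 0.35 bpm. I took every integer limit from 50 to 60, true rates 1-3 bpm either side of it, and two readings varying independently. Mean misclassification then falls from 5-15% to 0% (reading SD 0), from 15-18% to 12% (SD 2) and from 26-27% to 25% (SD 4).

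**The case against.** The strongest reply is that the protocol already covers the risk. Every escalated dose is followed by a timed 2-hour check. Section 2.3.2.1 adds that the response is generally greatest after the first dose, and that a normal first-dose reading needs no repeat at the same level, with exceptions for very young patients, those with cardiovascular problems or co-morbidities, and those with complaints. As to safety, this largely stands. A reader might infer that patients are being escalated unsafely; the text does not support that, because a falsely normal return-visit reading is followed by another at 2 hours. A reader might also infer that the Week 8 value is uninterpretable. That goes too far: patients on 3 mg/kg/day have passed the 2-hour check, and an off-peak Week 8 reading is only less sensitive. The reply does not reach the false hold, since a held patient receives no escalated dose that could correct it.

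Item e of 6.1.1.1 might suggest that one badly timed reading ends therapy. A patient still on 0.5 mg/kg/day at Week 4 has normally failed or been held already, so that rule usually acts on a second event.

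The word baseline in section 2.4 makes a pre-dose reading the more natural intent, because a new dose at the visit would otherwise sit on top of a recent home dose. That is inference; the instruction is absent.

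The effect is also probably small. Table 7 lists asymptomatic hypotension at 2.8% and asymptomatic bradycardia at 0.9%. Their sum, 3.7%, over 15-20 patients is about 0.6-0.7 patients. These are infantile haemangioma data and do not count near-limit patients, so they give scale only. Entry also requires normal heart rate and blood pressure (4.1.7.4).

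Finally, pre-dose gating has a cost of its own: by the model above, it is less likely to show a fall on the continuing dose. That stands, and is dealt with in the fix.

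**Conclusion.** The gap is real: readings that decide escalation, and the Week 8 reading, are judged against one limit with no set time since the dose. Its effect is confined to patients near the limit, whose number is unknown and probably small. For such a patient, one hold driven by timing removes the chance of reaching 3 mg/kg/day in the study. The probabilities rest on an assumed 3-10 bpm difference and an assumed SD of 2-6 bpm. The absence of timing and the 2 mg/kg/day cap come from the text and need no assumption. Appendix 7 (normal ranges) and Appendix 1 (forms, which might record dose time) were not available. This is a minor improvement to the consistency of the tolerability data, worth making because it costs little.

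**What to change.** - In 5.2.2 and 6.1.1, have patients hold the morning dose on Week 2, 4 and 6 visit days. Take the gating vital signs pre-dose, give the escalated dose as that morning's dose, and keep the 2-hour check. This also avoids stacking the new dose on a recent home dose.
- Take Week 8 vital signs about 2 hours after a dose.
- In 2.4 and 5.2.2, apply the 2-hour check explicitly to the first 0.5 mg/kg/day dose.
- Record the clock time of the last dose at each visit, unless the Appendix 1 forms already do.
- Because pre-dose readings are less sensitive to falls on the continuing dose, state that tolerability at each dose rests mainly on the timed 2-hour readings.
- Separately, replace the 15-second pulse count in 6.1.1 with 60 seconds. The gain is small when visit-to-visit variation is large.

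The cost is one dosing instruction, at most one data field, and 45 seconds more per pulse count. Patients already wait 2 hours after an escalated dose. Week 8 may add a short wait, which fits within the 3-4 hour body-water test (11.3.2) if both are done the same day and the dose is compatible with the fast. Visits need to be in the morning so that the held dose is not long delayed. A few patients will receive one supervised higher dose before the 2-hour check stops escalation.
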